12.1.2 Comparisons within YAPHIV

For the second type of comparison, subgroups of the YAPHIV will be examined. For example, comparisons can be made between those YAPHIV who initiated ART before age 5 vs. those who initiated ART at a later age. The table below summarizes the detectable differences in means relative to the standard deviation that can be detected assuming 650 YAPHIV or 415 participants (under an assumption of 4% loss per year) when two subgroups of the YAPHIV are being compared.

Table 12.2. Detectable differences in means (relative to SD) between subgroups of YAPHIV

Comparison Between Group 1 and Group 2, with indicated percentage in each group		Detectable Differences in Means (Relative to SD)	
Group 1	Group 2	N = 650	N = 415
50%	50%	0.220	0.276
40%	60%	0.224	0.281
30%	70%	0.240	0.301
20%	80%	0.275	0.345
10%	90%	0.366	0.462

Similarly, proportions with events between two subgroups of YAPHIV could be compared; for example, defined by prior receipt of cART with PI vs. cART without PI, or use of a specific ARV drug vs. unexposed to that drug. The following table provides the minimum detectable differences in terms of ORs.

Table 12.3. Detectable differences in ORs based on logistic regression models comparing two subgroups of YAPHIV with N = 650 participants or N = 415

Percent in Each group		Event Rate in Group 2	OR for Given Sample Size	
Group 1	Group 2		N = 650	N = 415
50%	50%	4%	2.59	3.20
		5%	2.38	2.89
		10%	1.93	2.25
		20%	1.68	1.90
		40%	1.56	1.75
40%	60%	4%	2.73	3.43
		5%	2.49	3.07
		10%	1.99	2.33
		20%	1.71	1.94
		40%	1.58	1.77
30%	70%	4%	3.02	3.92
		5%	2.73	3.45
		10%	2.11	2.53
		20%	1.78	2.05
		40%	1.63	1.84
20%	80%	4%	3.69	5.06
		5%	3.25	4.33
		10%	2.39	2.96
		20%	1.95	2.30
		40%	1.75	2.02

In evaluating both continuous outcomes and binary outcomes, greater power will be attained in longitudinal analyses of repeated measures over time.

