12.1 Power and Sample Size Consideration

In the context of this study, many targeted outcomes, some continuous (e.g., BMI, and height and weight z-scores) and some binary (insulin sensitivity, and neurodevelopmental impairment) will be measured.

For relatively rare events, the calculations for binary outcomes can serve as good approximations for survival outcomes, and for more common outcomes they often serve as an upper bound (i.e., a survival analysis would have greater power than comparison of proportions of events at a fixed time). All of the following calculations were conducted using PASS 15.0.4 (NCSS, 2017).

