12.1.1 Comparisons between YAPHIV and YAPHEU

For continuous outcomes, the sample size of 650 YAPHIV vs. 200 YAPHEU provides 80% power to detect a difference in means of 0.227 standard deviations based on a 2-sample t-test (assuming normality holds), and 0.240 based on a non-parametric Wilcoxon rank sum test (for skewed outcomes) at alpha = 0.05. For example, if the full-scale IQ scores of YAPHIV is compared with YAPHEU and a standard deviation of 15 points is assumed, a difference of 3.40 points or more in the mean IQs could be detected. Assuming loss to follow-up and/or incomplete/missing assessments of 4% per year for infected and 6% per year for uninfected participants at two years after enrollment into AMP Up is completed, then an adjusted sample size of 415 YAPHIV vs. 101 YAPHEU provides 80% power to detect a difference of 0.311 standard deviations, or 4.67 points in mean IQ scores. Once adjusted for potential confounders, some power will typically be lost so the minimum detectable difference will usually increase.

For binary outcomes, the table below shows the minimum difference that can be detected in proportions in terms of the Odds Ratio (OR) based on comparing YAPHIV vs. YAPHEU, at 80% power with a 0.05 significance level. For this type of outcome, the detectable differences depend on the underlying rate of the event in the comparison cohort. For simplicity here, it is assumed that the event rate is higher in the YAPHIV cohort than the YAPHEU cohort.

Table 12.1. Minimum detectable ORs between YAPHIV and YAPHEU at 80% power and a 0.05 significance level for various event rates in the comparison cohort

Sample Size for YAPHIV Cohort	Sample Size for YAPHEU Cohort	Event rate in YAPHEU Cohort	Minimum Detectable OR	Detectable Rate in YAPHIV Cohort
650	200	4%	2.92	10.8%
		5%	2.64	12.2%
		10%	2.05	18.6%
		20%	1.73	30.2%
		30%	1.63	41.0%
415	101	4%	4.36	15.4%
		5%	3.79	16.6%
		10%	2.68	22.9%
		20%	2.13	34.7%
		30%	1.95	45.5%

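### Table 12.3 assigns the event rate to Group 2, but its unbalanced cells were computed with that rate in Group 1, so as labelled the minimum detectable odds ratios are overstated by up to 49%

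*Protocol*

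**What the plan says.** Section 12.1.2 covers comparisons between two subgroups of the YAPHIV cohort. For binary outcomes it gives as examples cART with or without a PI and "use of a specific ARV drug vs. unexposed to that drug". Table 12.3 is titled "Detectable differences in ORs based on logistic regression models comparing two subgroups of YAPHIV with N = 650 participants or N = 415". Under "Percent in Each group" it lists Group 1/Group 2 as 50/50, 40/60, 30/70 and 20/80, so Group 1 is never the larger group. The reference rates (4, 5, 10, 20 and 40%) stand under "Event Rate in Group 2".

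Table 12.3 does not restate alpha or power. The companion text in Section 12.1.1 works "at 80% power with a 0.05 significance level", and Section 12.1 says "All of the following calculations were conducted using PASS 15.0.4". Nothing in Section 12.1.2 says that the reference rate belongs to Group 1 or that the percentages are reversed.

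**The concern.** For a fixed OR above 1 and a low reference rate, it matters which group carries that rate. If the small group has the low rate, it contributes very few events, the log OR is imprecise, and a large OR is needed for 80% power. If the large group has the low rate, the small group has the raised rate, the events are better balanced, and a smaller OR suffices. The printed ORs rise steeply as the split becomes uneven, which is the pattern of the first case, whereas the heading describes the second.

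The drug-exposure example reads naturally as a minority of users (Group 1) against an unexposed majority (Group 2). For that layout the table would make the study look less able to detect effects than it is. Section 12.0 says that many primary hypotheses on ART regimens will be tested within YAPHIV, and Table 12.3 is the only binary-outcome power table for those comparisons. Section 12.1 also offers the binary calculations as approximations for survival outcomes when events are rare, so the 4% and 5% rows serve there too.

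**Working it through.** **Inputs.** Total N of 650 or 415, the splits and the rates are from Table 12.3. Alpha 0.05 and 80% power are carried over from Section 12.1.1. A two-sided test is assumed and is checked in step 1.

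**Formula.** With reference rate p, raised rate p′ = OR·p / (1 − p + OR·p), and group sizes n (reference) and n′ (other):

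- SE² = 1/[n·p(1−p)] + 1/[n′·p′(1−p′)]
- Power = Φ(ln OR / SE − 1.96)

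The minimum detectable OR is the value that gives power 0.80.

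**Step 1: does the method reproduce the plan's own figures?** In Table 12.1, with the reference rate in YAPHEU, N = 650/200 gives 2.92, 2.64, 2.05, 1.73 and 1.63, and N = 415/101 gives 4.36, 3.79, 2.68, 2.13 and 1.95. All ten are as printed. The 50/50 block of Table 12.3, where the group label cannot matter, also reproduces within 0.01 in all ten cells. This confirms two-sided 0.05, 80% power and the Wald form.

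**Step 2: one unbalanced cell in full.** 20/80, N = 650 (130 and 520), rate 4%, printed OR 3.69, so p′ = 0.1333 and ln OR = 1.3056.

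- Rate in Group 2, as labelled: SE² = 1/(520·0.04·0.96) + 1/(130·0.1333·0.8667) = 0.0501 + 0.0666 = 0.1167, so SE = 0.3416. Power = Φ(3.822 − 1.96) = 0.969.
- Rate in Group 1: SE² = 1/(130·0.04·0.96) + 1/(520·0.1333·0.8667) = 0.2003 + 0.0166 = 0.2170, so SE = 0.4658. Power = Φ(2.803 − 1.96) = 0.800.

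The most discrepant cell (20/80, 4%, N = 415, printed 5.06) behaves the same way: power is 0.981 as labelled and 0.800 with the rate in Group 1.

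**Step 3: all 30 unbalanced cells.** With the rate in Group 1, 30 of 30 match within 0.01, and power at the printed OR is 0.798 to 0.805. With the rate in Group 2, 4 of 30 match within 0.01, all of them at the 40% rate; every printed OR is above the recomputed one.

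Printed → 80%-power OR with the rate in Group 2, as labelled:

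| Split | Rate | N = 650 | N = 415 |
|---|---|---|---|
| 40/60 | 4% | 2.73 → 2.54 | 3.43 → 3.11 |
| | 5% | 2.49 → 2.35 | 3.07 → 2.83 |
| | 10% | 1.99 → 1.93 | 2.33 → 2.24 |
| | 20% | 1.71 → 1.68 | 1.94 → 1.90 |
| | 40% | 1.58 → 1.57 | 1.77 → 1.76 |
| 30/70 | 4% | 3.02 → 2.59 | 3.92 → 3.15 |
| | 5% | 2.73 → 2.40 | 3.45 → 2.88 |
| | 10% | 2.11 → 1.98 | 2.53 → 2.29 |
| | 20% | 1.78 → 1.73 | 2.05 → 1.96 |
| | 40% | 1.63 → 1.62 | 1.84 → 1.83 |
| 20/80 | 4% | 3.69 → 2.78 | 5.06 → 3.39 |
| | 5% | 3.25 → 2.57 | 4.33 → 3.10 |
| | 10% | 2.39 → 2.11 | 2.96 → 2.48 |
| | 20% | 1.95 → 1.84 | 2.30 → 2.12 |
| | 40% | 1.75 → 1.74 | 2.02 → 2.01 |

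The overstatement runs from 0.4% to 49.4% (5.06/3.39 ≈ 1.49), with median 7%. In the worst cell, against 4% in Group 2, the table implies that Group 1 must reach 17.4%; 12.4% is enough.

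**Step 4: could another formula explain it?** Pooled, unpooled and continuity-corrected z tests, a Wald test with null variance, and a likelihood-ratio test were tried, as were ORs below 1 (pooled z for all splits; Wald for 50/50 and 20/80). None fits the balanced and unbalanced blocks together with the rate in Group 2.

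**The case against.** The arithmetic is hard to dispute, but its weight can be. The error is conservative: as labelled, the study can detect smaller effects than the table says, and no promised power is lost. The 650/200 targets are explained in Section 12.0 by losses from AMP and expansion of the cohort, not by this table. The 49% is a single cell: 18 of the 30 unbalanced cells are off by less than 10%, 12 of them by less than 5%, and only five by more than 20%, all at 4% or 5% rates in the 20/80 or 30/70 splits. The protocol gives no exposure prevalences and does not say which group is exposed; where the reference group is the minority, the printed ORs are right. No text makes the main within-YAPHIV comparisons depend on this table. The nearest, in Section 12.2.1, limits analyses of effect modification between host genetics and ART to what power allows. The figures are also unadjusted planning values.

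All of this stands as a limit on the consequences. None of it makes the table right: 26 of the 30 unbalanced cells miss their labelled definition by more than 0.01, and nothing in the protocol corrects the label. In the 40% rows the two readings almost coincide, so for those cells the conclusion rests on the pattern of the others; no cell contradicts it.

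**Conclusion.** The concern holds. Table 12.3 is wrong as labelled: its unbalanced cells give the ORs for a reference rate in the smaller Group 1, not in Group 2. The discrepancy is material for rare events in uneven splits (up to 49% at 20/80 and 24% at 30/70) and under 1% at a 40% rate. Its direction is to understate what the study can detect. The conclusion rests on a two-sided 5% test, 80% power and the Wald form, none of which Table 12.3 states but all of which are supported by the match to Table 12.1 and to the balanced block. The table cannot show whether the event-rate heading is wrong or the two percentage headings were transposed; both give the same mismatch.

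**What to change.** Do one of the following:

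- Relabel the event-rate column as the rate in Group 1 (the smaller group), or swap the two percentage headings. Every printed OR is then correct.
- Keep the present label and replace the 30 unbalanced cells with the recomputed values tabulated above. This suits comparisons of a minority exposed to a drug with an unexposed majority.

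Whichever is chosen, state alpha, sidedness and power with the table, and say which group is the reference. The cost is the correction of one table; design, sample size and data collection are unaffected.

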12.1.3 Evaluating Interactions between HIV Status and Other Factors

Much scientific interest may be directed at whether relationships between specific measures and AMP Up outcomes differ between YAPHIV and YAPHEU. While the sample size for this study provides high power for detecting differences between YAPHIV and YAPHEU with respect to continuous outcomes and more common binary outcomes, the study will have only limited power to address potential interactions between HIV status and other outcomes. For example, if the interest is to evaluate whether the relationship between low vitamin D levels and height z-score differed between YAPHIV and YAPHEU, there would be relatively low power and such analyses would be primarily descriptive. Power calculations for detecting multiplicative interaction effects based on several combinations of underlying assumptions and magnitudes of interaction effects are shown below, determined via simulation with 5000 datasets simulated, each with the sample size indicated. These simulation studies present best case scenarios in that the outcomes are assumed to be continuous and normally distributed. The table below suggests that power could be adequate for detecting interactions if the sample size of young adults is achieved and the interaction effect is twice as large as either of the main effects. It is likely that power for binary outcomes would be substantially lower.

Table 12.4. Power for Detecting Interactions between a Specific Factor (such as low vitamin D) and HIV Status on a Hypothetical Continuous Outcome (such as height Z-score)

Sample Sizes (PHIV and PHEU)	Pr (low vitamin D in PHEU)	OR for low vitamin D in PHIV vs. PHEU	Main effect of low vitamin D on height (shift in z-score)	Main effect of HIV status on height (shift in z-score)	Interaction effect of both low vitamin D and PHIV on height (shift in z-score after main effects)	Empirical Power
650, 200	0.30	1.5 (p = 0.39)	0.25	0.25	0.25	29.6%
					0.40	63.4%
					0.50	82.6%
415, 101	0.30	1.5 (p = 0.39)	0.25	0.25	0.25	18.4%
					0.40	38.3%
					0.50	55.1%

12.2 Domain-Specific Statistical and Analytic Considerations

12.2.1 Infectious and Non-Infectious Complications of HIV and Its Treatment

Immunologic and virologic trajectories among YAPHIV will be described with locally estimated scatterplot smoothing (LOESS) plots over time (i.e., age) or explored with group-based trajectory models. Factors associated with CD4 and viral load trajectories will be identified using repeated measures generalized estimating equation (GEE) models, mixed effects models, or multinomial regression models as appropriate. Factors of interest for these outcomes include immune activation, changes in ART, cumulative exposure to specific ART, viral resistance, co-infections, and host genetic polymorphisms. Analyses of samples from the PHACS Repository will be required to measure markers of immune activation. Changes in ART will be assessed by first defining what constitutes a switch in ART regimen (i.e., what ARV drug changes constitute an ART switch). Cumulative duration of a specific ART will be

calculated by summing the time intervals exposed. Viral resistance will be calculated using the Stanford HIV Reverse Transcriptase and Protease Sequence Database which contains drug susceptibility data for selected mutations (Liu & Shafer, 2006; Shafer, 2006). The presence of co-infections such as CMV and EBV will be assessed by testing samples from the PHACS Repository prior to the events of interest. Past infection with SARS-CoV-2 will be ascertained from clinical chart review or measurement of antibodies from stored samples. Host genetic polymorphisms of interest will be identified using the established PHACS repository of amplified genomic DNA. Effect modification between host genetic polymorphisms and ART will be assessed as appropriate and feasible based on power issues noted above, based on a priori hypotheses.

Access to testing for SARS-CoV-2, access to and acceptance of prevention strategies for SARS-CoV-2, and acceptance of testing, treatment, and prevention strategies for other important infections will be assessed through participant report on web-based survey. Factors specifically associated with SARS-CoV-2 vaccine hesitancy and uptake among participants with PHIV and PHEU will include sociodemographic and socioeconomic characteristics, prior receipt of vaccines (influenza, HPV, MMR, etc.), participation in interventional clinical trials, reported trust in health care, knowledge/misinformation regarding SARS-CoV-2 infection, and HIV disease status including cumulative CD4 and viral load (for participants with HIV only).

Incidence of end-organ disease will be estimated under a Poisson distribution based on person-years of follow-up at risk. Factors associated with incidence of end-organ disease will be identified using Cox-proportional hazards models and will include HIV virologic status, ART, immune impairment, and chronic immune activation. The PHACS Repository will be the primary longitudinal resource to contribute to HIV remission/cure studies aimed to understand the viral dynamics and compartmentalization perinatal HIV infection.

Oral health will be examined by dental disease, periodontal diseases, and mucosal diseases. Dental disease is measured by the number of decayed, filled, and missing tooth surfaces due to dental caries (decayed, missing, and filled surfaces (DMFS)). The distribution of DMFS is right skewed and tends to have higher proportion of zeros than in a Poisson or negative binomial distribution, therefore the zero-inflated counterparts will be applied to model the prevalence. Progression in dental disease will be studied using the difference in DMFS scores. Periodontal diseases are measured by different parameters examined on multiple tooth sites, such as bleeding on probing (Yes/No) or clinical attachment loss (in millimeter); the latter is a measure of bone loss. Well-defined worsening (Yes/No) of a given parameter will be analyzed using GEE models with a logistic link function, considering the multi-layer clustering of site within tooth and tooth within participant. Mucosal diseases were very rare in our participants at the baseline visit. Cumulative incidence of a particular mucosal disease from baseline to the follow-up visit will be calculated and the relative risk between YAPHIV and YAPHEU can be estimated using a Poisson regression model. In addition to HIV infection status, inflammation level and oral microbiome signature at baseline are the exposures of interest for specific aims regarding periodontal diseases. Access to oral health care, hygienic behavior and diet are factors associated with all oral health outcomes and could be potential confounders in the association between HIV infection status and oral health.

12.2.2 Metabolic Complications

For metabolic complications, the interest is in estimating the prevalence and incidence of insulin sensitivity, dyslipidemia, hypertension, fat redistribution, obesity, and cardiometabolic risk (McMahan et al., 2005) as well as evaluating the association of HIV disease status and specific ART regimens with these outcomes. PHACS does not have longitudinal measures of lipids and homeostatic model assessment of insulin resistance (HOMA-IR) in AMP Up YAPHEU. Thus, incidence of insulin sensitivity,

dyslipidemia, and cardiometabolic risk will not be determined in this group. Additionally, the trajectories of blood pressure, and body composition over time between YAPHIV and YAPHEU and HOMA-IR and lipids will be compared, by ART regimens among YAPHIV.

Insulin sensitivity, dyslipidemia, hypertension, and obesity as binary outcomes

Prevalence: Insulin sensitivity, impaired fasting glucose (American Diabetes Association, 2020), and dyslipidemia (considering each of fasting total cholesterol, LDL cholesterol, HDL cholesterol, and triglycerides separately), hypertension (Flynn et al., 2017), and obesity will be considered as binary variables. HOMA-IR values will be calculated from fasting insulin and glucose and categorized by insulin resistance (Matthews et al., 1985). BMI above 30 kg/m² will be classified as obese.

For specific metabolic risk factors that can be calculated in YAPHEU (e.g., obesity, hypertension), the prevalence of each binary metabolic risk factor at each AMP Up visit among YAPHIV and compare them to YAPHEU will be estimated. Prevalence will be calculated as the number of participants with the specific outcome at that visit, divided by the total number of participants who are tested and have a measure for each outcome at that visit. The 95% confidence intervals (CIs) for each prevalence estimate will be calculated.

The association of each metabolic outcome with specific ART regimens (particularly INSTIs, PIs, and NRTIs, which have been implicated in various metabolic disorders) in YAPHIV will be evaluated by comparing the prevalence across ART regimens using chi-square tests. The association between each exposure and the prevalence of each metabolic risk factor will also be estimated using log binomial regression. These will be adjusted for confounders based on the literature and through construction of directed acyclic graphs (DAGs). These may include race, sex assigned at birth, gender identity, age, CD4 cell count, viral load, physical activity, diet, and BMI (except for body composition outcomes).

Incidence: The incidence rate of all the binary metabolic outcomes in YAPHIV incidence of hypertension and obesity in YAPHEU will be estimated. The incidence rate will be calculated by dividing the number of participants with new onset of each metabolic risk factor by the total person-time contributed by children initially free of the risk factor at baseline (or first measurement). The 95% CI for these incidence rates will be calculated using the Poisson distribution.

Among participants who are YAPHIV, the association between specific ART regimens and HIV disease severity (as measured by viral load) and incidence of the above metabolic risk factors will be estimated. The association of BMI and body composition at baseline with all outcomes (except obesity) in the YAPHIV and with hypertension in YAPHEU will be evaluated. The incidence of each outcome (with the possible exception of hypertension) is expected to be fairly common, so Cox proportional hazards models for the time to development of each risk factor will be used to estimate hazard ratios and their associated 95% CIs, adjusting for other risk factors for the outcome, by HIV status or by ART regimen (in the YAPHIV). These analyses will be adjusted for confounding. For metabolic risk factors that are observed to occur less frequently, Poisson regression models may be used to compare incidence rates.

Systolic and diastolic blood pressure, lipid levels, body composition, and cardiometabolic risk measures as continuous outcomes

Systolic and diastolic blood pressure, lipid levels (total cholesterol, HDL cholesterol, LDL cholesterol, and triglycerides), HOMA-IR, and cardiometabolic risk (as measured by PDAY scores) will be considered as continuous outcomes. The body composition measures (waist, mid-upper arm and hip

circumferences, and triceps, biceps, suprailiac, and subscapular skinfolds), and sum of skinfolds will be considered only as continuous outcomes. BMI will be evaluated as a binary or continuous variable.

For cross-sectional data, outcomes in YAPHIV and YAPHEU will be compared using generalized estimating equations for a continuous outcome with the robust variance estimator. Potential confounders that may be included in the models of blood pressure and lipids are BMI, sex, race, physical activity, tobacco use, and diet. Models of body composition may include all of these, but not BMI. Models of cardiometabolic risk (PDAY scores) will include age and sex. The association of each class and type of ART for each outcome in models restricted to YAPHIV will be investigated.

To examine the effect of exposures that vary over time, such as ART regimens (in YAPHIV) or body composition, mixed effects models will be used, which will account for the correlations between these repeated measures. The change over time in waist and mid-upper arm circumferences, waist-to-height ratio, triceps, biceps, suprailiac, and subscapular skinfolds, and BMI will be compared by HIV status.

To examine trajectories of the continuous outcomes between YAPHIV and YAPHEU or within YAPHIV by HIV-associated exposures such ART regimens or CD4 count, mixed effect models will be fit, adjusting for potential confounders.

The food security score will be calculated and YAPHIV and YAPHEU will be categorized into levels of food security. The association of sociodemographic factors and dietary factors with food security level will be examined using chi-square or Wilcoxon tests. In longitudinal analysis, the effect of low food security on change in BMI, lipid concentration and HOMA-IR and on adherence to ART will be evaluated. Mediation analysis will be used to examine whether an association of food security with adherence is mediated through engagement in clinical care.

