2.2.2 Metabolic Complications

Specific Aim:

- To evaluate longitudinal changes in parameters of cardiometabolic risk by HIV status (YAPHIV vs. YAPHEU), including body weight and composition, lipid levels, insulin sensitivity, blood pressure, and modified PDAY scores (a predictor of atherosclerosis).
- Among YAPHIV, to evaluate the association of ART switches with changes in body weight and composition, lipid levels, insulin sensitivity, and blood pressure.
- To evaluate food security and diet in YAPHIV and YAPHEU and their associations with body composition and metabolic outcomes. Among YAPHIV, to evaluate the association of food

security with adherence to ART and whether the association is mediated through engagement in clinical care.

Hypotheses:

- YAPHIV will manifest parameters of increased cardiometabolic risk, with unfavorable trajectories compared to YAPHEU.
- Switching to newer-line ART will result in improvement in some but not all parameters of cardiometabolic risk.
- YAPHIV will have greater food insecurity than YAPHEU, and YAPHIV with food insecurity will be more likely to be obese, have poorer metabolic outcomes, and be less likely to engage in clinical care.
- YAPHIV with food insecurity will have poorer adherence to ART medications that is mediated through engagement in care.

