Annual Web-Based Survey ³	The following categories of questions will be included in the annual surveys: socio-demographics, general health and health care-related, mental health, social determinants of health, reproductive health, sexual behaviors, and substance use.											To be completed on any device with access to the internet, including a cell phone. Most questions are part of a single primary survey, but some may be administered separately as a short, stand-alone survey.
Additional Web-based Surveys	In addition to the evaluations specified in the protocol, completion of occasional brief voluntary web-based or interview-administered surveys by participants may be requested to address specific time-sensitive or important issues as they arise. The content of these additional surveys will fall under the aims of the protocol and be covered by the informed consent, with notification of the HLC IRB as required.											
Chart Abstraction⁴												
Interval diagnoses, medications ⁵ , and family history	X	X	X	X	X	X	X	X	X	X	X	
Results of lab tests conducted for clinical care ⁶	X	X	X	X	X	X	X	X	X	X	X	
Height, weight, and blood pressure	X	X	X	X	X	X	X	X	X	X	X	

	Entry (Year 0) ¹	Year										Comments
		1	2	3 ¹	4	5	6 ¹	7	8	In-person visits (9, 12...) ¹	Years without in- person visits (10, 11, 13, 14...)	
Laboratory: Real-Time Testing												
STI testing ⁷	X	X	X	X	X	X	X	X	X	X	X	--Self-collect in clinic at Entry and the in-person follow-up visits (e.g., Years 3, 6, 9, 12...) --Self-collect at home and deliver/mail to clinic at all other years --Do not perform if results are available for both N. gonorrhoeae and C. trachomatis within the past 12 months --Males: urine --Females: vaginal swab #1 or urine if swab is declined
HIV test ⁸				X					X			Also abstract results for any test conducted after the Entry visit
Laboratory: Central Testing⁹												
Urine for renal biomarkers	X			X			X			X		Collect in clinic
Serum for cardiac biomarkers	X			X			X			X		Collect in clinic
Fasting serum lipids	X			X			X			X		Collect in clinic
Fasting plasma glucose and serum insulin	X			X			X			X		Collect in clinic
Research Aptima STI testing ¹⁰	X	X	X	X	X	X	X	X	X	X	X	--Self-collect in clinic at Entry and the in-person follow-up visits (e.g., Years 3, 6, 9, 12...) --Self-collect at home and deliver/mail to clinic at all other years --Males: urine Females: vaginal swab #2 or urine if swab declined
Repository												

	Entry (Year 0) ¹	Year										Comments

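### Section 12.2.2 sets aside repeat lipid and HOMA-IR data in YAPHEU that Appendix II schedules and the first metabolic aim needs, and contradicts itself on the between-cohort trajectories

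*Protocol*

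**What the plan says.** Section 12.2.2 opens with a premise about the comparison cohort: "PHACS does not have longitudinal measures of lipids and homeostatic model assessment of insulin resistance (HOMA-IR) in AMP Up YAPHEU". Two restrictions follow. Incidence of insulin sensitivity (that is, insulin resistance), "dyslipidemia, and cardiometabolic risk will not be determined in this group". For trajectories, only blood pressure and body composition are set against YAPHEU, while "HOMA-IR and lipids will be compared, by ART regimens among YAPHIV". The later incidence paragraph keeps to this: all the binary metabolic outcomes are followed in YAPHIV, but for the comparison cohort only the "incidence of hypertension and obesity in YAPHEU will be estimated".

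Three other places say something different.

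- Appendix II, the YAPHEU schedule, lists "Fasting serum lipids" and "Fasting plasma glucose and serum insulin" under central testing. Both are marked at Entry, Years 3 and 6, and the later in-person visits (9, 12 and so on).
- The first aim in Section 2.2.2 is "To evaluate longitudinal changes in parameters of cardiometabolic risk by HIV status (YAPHIV vs. YAPHEU), including body weight and composition, lipid levels, insulin sensitivity", and it goes on to blood pressure and modified PDAY scores. Its first hypothesis is about trajectories relative to YAPHEU.
- The continuous-outcome part of Section 12.2.2 names lipids, HOMA-IR and PDAY scores as continuous outcomes, then plans mixed models "To examine trajectories of the continuous outcomes between YAPHIV and YAPHEU or within YAPHIV by HIV-associated exposures".

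**The concern.** The reason given for leaving YAPHEU out of these analyses does not match what the protocol collects from YAPHEU. Lipids are measured directly, and Section 12.2.2 itself derives HOMA-IR from fasting insulin and glucose, which are on the same schedule.

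Two things are at stake. First, incidence of dyslipidemia, insulin resistance and raised cardiometabolic risk has no comparator, so a rate in YAPHIV cannot be set against one in YAPHEU. Section 1.1.3 gives separating HIV and ART effects from contemporary trends as the purpose of the comparison group, and a comparison of ART regimens within YAPHIV cannot serve that purpose. Second, the instruction on trajectories is ambiguous. One analyst could follow the opening paragraph and omit the cohort comparison for lipids and HOMA-IR. Another could follow the mixed-model paragraph and run it. In a study with many outcomes, that choice should not be left until the data have been seen.

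**Working it through.** The contradiction is textual and rests on no sample size. The sections compare as follows.

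| Item | Opening and incidence text of 12.2.2 | Elsewhere in the protocol |
|---|---|---|
| Repeat lipids in YAPHEU | Said not to exist | Appendix II: Entry, Years 3, 6, 9, 12 and on |
| Repeat HOMA-IR in YAPHEU | Said not to exist | Appendix II: fasting glucose and insulin at the same visits |
| Who gives the specimens | Not addressed | Appendix II footnote: all participants, including those who decline repository storage |
| Lipid and HOMA-IR trajectories by HIV status | Limited to ART regimens within YAPHIV | First aim and hypothesis in 2.2.2; mixed-model paragraph of 12.2.2 |
| Incidence by HIV status | YAPHEU: hypertension and obesity only | Cox models for each risk factor by HIV status or by ART regimen (same incidence text) |

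**Planned measurements.** A YAPHEU participant followed to Year 6 has 3 scheduled lipid and 3 scheduled glucose/insulin measurements (Entry, Years 3 and 6). One followed to Year 12 has 5. Two are enough to estimate change.

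**What survives.** Section 12.2.2 keeps a cross-sectional cohort comparison of the continuous outcomes. Section 12.2.3 compares the PDAY distribution by HIV status. Blood pressure and body composition trajectories by HIV status are planned consistently.

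**Illustrative precision.** The minimum detectable difference at 80% power and two-sided 0.05 is (1.960 + 0.842) × √(1/n₁ + 1/n₂), in SD units.

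- Check against Section 12.1.1. With 650 and 200: 2.80 × √(1/650 + 1/200) = 0.2265, stated as 0.227. With 415 and 101: 2.80 × √(1/415 + 1/101) = 0.3108, stated as 0.311. Both reproduce.
- Year 3, using that section's yearly losses of 4% and 6%: 650 × 0.96³ = 575 and 200 × 0.94³ = 166. The detectable difference is 2.80 × √(1/575 + 1/166) = 0.247.
- Year 6: 650 × 0.96⁶ = 509 and 200 × 0.94⁶ = 138, giving 0.269.

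For a trajectory comparison the unit is the SD of the change score, not the cross-sectional SD behind the figures in 12.1.1.

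**The case against.** The best defence is that the premise describes data in hand. It is in the present tense, in a protocol for a cohort already running: Section 1.1 reports 124 YAPHEU from AMP already enrolled, Section 4.6 refers to participants enrolled under version 1.0, and Section 12.0 says most analyses draw on historical data. The version 1.0 YAPHEU schedule is not shown, so early enrollees may lack Entry fasting values. This stands as a possibility, and it means the premise cannot be called false for every YAPHEU participant. It does not remove the conflict. The text names no affected visits or participants, and it carries the exclusion forward to analyses not yet done.

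A second objection also stands. A reader might infer that the whole between-cohort comparison is discarded and that the first metabolic aim cannot be answered for these outcomes. The documents do not support that. The mixed-model paragraph would restore the trajectory comparison, the cross-sectional comparisons remain, and other named parts of the aim are unaffected.

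Third, 575 and 166 are not the plan's figures. They assume full target enrollment and that everyone retained has fasting samples at both visits. Section 5.0 treats blood draws as missed at remote visits (unless made up later with approval), Section 8.3 provides no laboratory work for participants followed centrally, and Section 9.7 allows fasting to be waived. The protocol's own loss-adjusted sizes are 415 and 101, and Section 12.1.1 warns that confounder adjustment usually raises the detectable difference.

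**Conclusion.** The concern holds as an internal contradiction with a limited consequence. Section 12.2.2 excludes YAPHEU from lipid and HOMA-IR analyses on a premise that the current YAPHEU schedule does not bear out. That exclusion conflicts with the first metabolic aim and hypothesis, and with the section's own mixed-model paragraph. The loss is incidence of dyslipidemia, insulin resistance and cardiometabolic risk in YAPHEU, and an unambiguous longitudinal comparison of lipids, HOMA-IR and PDAY scores by HIV status.

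The size can only be illustrated. About 0.25 SD of the change score would be detectable if 575 YAPHIV and 166 YAPHEU had both Entry and Year 3 values, and about 0.31 SD with 415 and 101. Both are unadjusted and ignore missed fasting draws. The conclusion does not depend on either figure. It rests on Appendix II being the schedule in force for all YAPHEU from this version on, and it leaves open that some earlier enrollees lack early measurements.

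**What to change.** In the opening paragraph of Section 12.2.2, remove three things: the premise that YAPHEU have no repeat measures, the exclusion of YAPHEU incidence, and the restriction of lipid and HOMA-IR trajectories to YAPHIV. In the incidence paragraph, extend YAPHEU incidence from hypertension and obesity to dyslipidemia, insulin resistance and cardiometabolic risk.

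Then state that incidence and mixed-model trajectories of lipids, HOMA-IR and PDAY scores are compared by HIV status among participants with at least two fasting measurements. Incidence is taken among those free of the condition at their first measurement. Where Entry values are missing, time starts at the first AMP Up fasting sample.

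If some YAPHEU, such as those enrolled under version 1.0, truly lack these measures, say which participants or visits are affected and limit the comparison to those with data. Label any precision figure as illustrative and give its assumptions.

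The cost is protocol and analysis-plan wording and a modest amount of extra analysis. No sample, visit or assay is added, because collection and central testing are already scheduled.
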